5.2 Secondary Efficacy Endpoints

- Time to stable housing after randomization
- Proportion of families who obtain stable housing during the 24-month intervention period
- Proportion of families who retain stable housing in the 12 months following the end of the 24-month intervention period
- Number of days spent living in a homeless shelter, in a place not typically used for sleeping, such as on the street, in a car, in an abandoned building, or in a bus or train station, or temporarily in an institution
- Number of days spent residing in a hotel or motel as a form of temporary housing
- Number of days spent residing in a space without any legal right to the space (i.e., residing in a space without a lease)
- Number of days spent in a shared living situation intended to be temporary (‘doubled up’ with a friend or relative due to being unable to find or afford own housing)

- Proportion of people experiencing homelessness for ≥ 1 night during study period
- Proportion of people living in a homeless shelter, in a place not typically used for sleeping, such as on the street, in a car, in an abandoned building, or in a bus or train station, or temporarily, in an institution for ≥ 1 night during study period
- Proportion of people living in a hotel or motel as a form of temporary housing for ≥ 1 night during study period
- Proportion of people residing in a space without any legal right to the space (i.e., residing in a space without a lease) for ≥ 1 night during study period
- Proportion of people in a shared living situation intended to be temporary ('doubled up' with a friend or relative due to being unable to find or afford own housing) ≥ 1 night during study period
- Proportion of people with any return to a homeless shelter at any time after enrollment
- Changes in household composition
- Changes in employment status and household income
- Number of moves
- Overcrowding
- Housing condition, quality, and affordability (i.e., housing cost burden) through selected questions adapted from the American Housing Survey and Family Options Study
- Proportion of monthly income spent on housing-related expenses
- Monthly household expenditures and categories of expenditures, assessed through selected questions adapted from the US Bureau of Labor Statistics Consumer Expenditures Survey
- Physical well-being, as measured through the Short-Form 12 v2
- Psychological well-being, as measured through the Kessler 6
- Financial well-being, through selected questions adapted from the Consumer Financial Protection Bureau Financial Well-Being Scale and the Urban Institute Basic Needs and Well-Being Survey
- Material hardship as measured through selected questions from the Survey of Income and Program Participation and the Urban Institute Basic Needs and Well-Being Survey
- Food insecurity, as measured through the United States Department of Agriculture Household Food Insecurity Survey
- Agency, as measured through the 12-item Adult Hope Scale
- Self-efficacy, as measured through the Generalized Self-Efficacy Scale
- Perceived stress, as measured through the Perceived Stress Scale
- Household environment, as measured through the Chaos, Hubbub, and Order Scale

- Resilience, as measured through the Brief Resilience Scale
- Health conditions and functional status through self-report and administrative data when available
- Social service use through self-report and administrative data when available
- Health service use (including health insurance type) through self-report and administrative data when available
- How cash payments may interfere with vs enhance network strain and support, specifically in terms of the following domains, via semi-structured interviews:
 - Public benefits, services and/or assistance
 - Community and interpersonal relationships
 - Support of friends and family
- The impact of cash payments on time scarcity, self care, and social goods, via semi-structured interviews
- The rationale behind selection of preferred cash payment disbursement schedule, via semi-structured interviews
- The influence and perceived impact of preferred cash payment disbursement schedule on primary and secondary outcomes listed above, via semi-structured interviews
- Household needs not addressed or affected by receipt of cash payments and alternate strategies to meet those needs, via semi-structured interviews
- The long-term positive and adverse effects of cash payments, in the year following completion of the cash payments
- *Incidence of adverse events:* loss or reduction in public benefits, services and/or assistance directly resulting from receipt of cash payments

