Total duration of participant participation will be 36 months from the time of enrollment. Total duration of the study is expected to be 48 months (12 months for recruitment and 36 months for follow-up from the time of last participant enrolled).

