5 CRITERIA FOR EVALUATION

5.1 Primary Efficacy Endpoint

Our primary endpoint is number of days experiencing homelessness (with ‘homelessness’ as defined below in section 6.2) during the study period.

For our primary endpoint, number of days experiencing homelessness, given our sample size of 300 with 150 participants in each arm, we estimate that we will have 80% power at a two-sided significance level of 0.05 to detect a mean reduction of 24.0 days in the intervention group, assuming a mean of 52.3 ± 74.0 days experiencing homelessness from prior studies. Allowing for a 27% dropout rate as estimated from prior studies (for a total of sample size of 220 participants with 110 families in each arm), we will still have 80% power at a two-sided significance level of 0.05 to detect a mean reduction of 28.0 days in the intervention group.

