6.2 Inclusion Criteria

1. ≥ 18 years of age at baseline visit *and* has a child ≤ 17 years of age living in household.
2. A resident of Santa Clara County.
3. Experiencing homelessness, as defined by:
 - a. The Homeless Emergency Assistance and Rapid Transition to Housing Act (HEARTH Act) final rule on the definition of homelessness as published in the Federal Register in 2011; and/or
 - b. Living in a public or private space intended for temporary (≤ 6 month) residence, such as residing in a hotel/motel; residing in a space without a legal right to the

space and therefore being at threat of being asked to leave at any time (i.e., no lease or unleased); and/or being in a shared living situations intended to be temporary (i.e., being ‘doubled up’ due to lack of available and/or affordable housing).

4. Vulnerability-Index Service Prioritization Decision Assistance Tool (VI-SPDAT) score within the eligibility range for referral to rapid rehousing assistance programs in Santa Clara County (score of 4-8 for households), when available
5. Written informed consent (and assent when applicable) obtained from participant or participant’s legal representative and ability for participant to comply with the requirements of the study.

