8 STUDY INTERVENTIONS

8.1 Method of Assigning Participants to Treatment Groups

Up to 300 eligible participants will be randomly assigned to the guaranteed income group (intervention) or usual care (control group) using a computer-generated randomization scheme developed by the study team. Eligible participants will be referred by the community partners (DHSV and SSPC) to the study team for consent and enrollment into the study prior to randomization. Once participants are enrolled, they will undergo a baseline assessment before being randomly assigned to either the intervention or control group. Randomization will be stratified by referring community partner (DHSV vs SSPC). Group assignments will be known to our community partners at Sacred Heart Community Service, a neutral third community-based organization contracted by DHSV and SSPC to administer and provide support for the guaranteed income intervention; however, the core study team (investigators and core research staff at UCSF) will be blinded to group assignments.

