10 EVALUATIONS BY VISIT

10.1 Visit/Assessment 1: Baseline Survey Assessment (Month 0)

1. Review the study with the participant (participant's legal representative) and obtain written informed consent and HIPAA authorization and assent, if appropriate.
2. Assign the participant a unique screening number.
3. Record demographic data.
4. Record household composition data (number of household members and children).
5. Administer and record current housing situation and history of homelessness instruments, adapted from the Family Options Study and the California Statewide Survey on Homelessness.
6. Administer and record income and employment survey, adapted from the California Statewide Survey on Homelessness.
7. Record concomitant interventions in terms of receipt of assistance from other housing, social, and economic assistance programs.
8. Administer and record monthly expenditure amounts and categories, adapted from the Survey of Income and Participation.
9. Administer and record Financial Well-Being Scale, adapted from the Consumer Financial Protection Bureau (financial well-being).
10. Administer and record Material Hardship Survey, adapted from the Urban Institute Well-Being and Basic Needs and the Survey of Income and Program Participation (material hardship)
11. Administer and record the USDA Brief Food Security Survey (food security)
12. Administer and record healthcare utilization survey, adapted from the California Statewide Survey on Homelessness
13. Administer and record health conditions and functional status survey, adapted from the California Statewide Survey on Homelessness
14. Administer and record Short-Form 12 v2 (physical health)
15. Administer and record Kessler 6 (psychological health)
16. Administer and record the Generalized Self-Efficacy Scale (self-efficacy)
17. Administer and record the Brief Resilience Scale (resilience)
18. Administer and record the Perceived Stress Scale (perceived stress)

19. Administer and record the Confusion, Hubbub and Order Scale (household chaos)
20. Administer and record the Future Scale (aka the Adult Hope Scale) (agency)
21. Schedule participant for Visit 2 in 180-240 days
22. Randomize participant to study group
23. Connect participant with community partner organization (Sacred Heart Community Service) for further social service assessment and assistance (both control and intervention groups) and orientation/navigation for initiation of guaranteed income payments (intervention group)

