12.2 Withdrawal of Participants from the Study

A participant may withdraw from the study at any time if the participant, investigator or sponsor feel that it is not in the participant's best interest to continue. All participants are free to withdraw from participation at any time, for any reason, specified or unspecified, and without prejudice.

Reasonable attempts will be made by the investigator to provide a reason for participant withdrawals. The reason for the participant's withdrawal from the study will be specified

in the participant's source documents. As noted above, participants who discontinue study treatment early (i.e., they withdraw prior to the end of the 36-month study period) should have an early discontinuation assessment. Refer to Section 10 for early termination procedures assessment. Participants who withdraw after Visit/Assessment 4 but prior to Visit 5 should be encouraged to come in for a final visit (and the procedures to be followed would include those for their next scheduled visit).

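### The secondary endpoint of any homelessness during the study period is met by nearly every family at entry, so it cannot separate the arms

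*Protocol*

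**What the plan says.** Section 5.2 of the protocol includes, among the secondary efficacy endpoints, "Proportion of people experiencing homelessness for ≥ 1 night during study period". The item gives no start date, no washout and no condition that the family has first been housed.

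Four other statements fix how it will behave:

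- **Entry.** Inclusion criterion 3 in section 6.2 reads "Experiencing homelessness, as defined by", followed by a broad definition: the federal HEARTH Act rule, temporary residence such as a hotel or motel, occupying a space without a lease, or doubling up.
- **Outcome definition.** Section 5.1 defines homelessness for the primary endpoint "as defined below in section 6.2", which is the entry criterion itself.
- **Window.** Section 4.1 states "Total duration of participant participation will be 36 months from the time of enrollment". Section 12.2 refers to withdrawal "prior to the end of the 36-month study period". The term study period is not defined separately anywhere.
- **Order of events.** Section 8.1 says that once participants are enrolled "they will undergo a baseline assessment before being randomly assigned to either the intervention or control group". In section 10.1, randomization is item 22, and the hand-over to the partner organization that starts payments is item 23.

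Neighboring items in section 5.2 do carry a window or qualifier, for example "Proportion of families who retain stable housing in the 12 months following the end of the 24-month intervention period". The shelter item is worded as a return after enrollment.

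**The concern.** An endpoint that nearly every participant meets at entry carries almost no information about treatment. Here the entry condition and the outcome condition are the same, and the counting window appears to open on the day the entry condition is verified. The first homeless night would then usually precede randomization, and almost always the first payment.

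Two things are at stake. The item takes a place among the efficacy endpoints without answering the question it seems to ask, namely whether guaranteed income keeps families out of homelessness. And a result near 100% in both arms could be read as evidence of no effect, when it only reflects the eligibility rule.

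The concern is limited to this overall item. The four sub-type items (shelter or street, hotel or motel, no legal right to the space, doubled up) are only partly fixed by the sub-type in which a family enters, so they are not saturated in the same way.

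**Working it through.** **1. The plan's own figures.** The protocol gives no expected rate or power for this item. Its sample-size statement in section 5.1 supplies the arm sizes, and it reproduces. The detectable difference is (1.960 + 0.842) × SD × √(2/n), with SD 74.0 days:

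- n = 150 per arm: 2.802 × 74.0 × √(2/150) = 23.9 days (stated 24.0).
- n = 110 per arm: 2.802 × 74.0 × √(2/110) = 28.0 days (stated 28.0).
- Dropout of 27%: 300 × 0.73 = 219 (stated 220, or 110 per arm).

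**2. Expected proportion as worded.** Suppose time from enrollment to first being housed is exponential with mean m days (an assumption). The share with at least one homeless night is exp(−1/m):

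| Mean days to housing | Share with ≥ 1 homeless night |
|---|---|
| 30 | 96.7% |
| 52.3 | 98.1% |
| 180 | 99.4% |

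Even a sixfold difference in mean time to housing (30 against 180 days) moves the endpoint by only 99.4 − 96.7 = 2.7 points.

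**3. Event-free families needed for significance** (two-sided Fisher exact test). With none among the controls and k in the intervention arm, p = 2 × C(n,k)/C(2n,k). For n = 150, k = 5 gives 0.060 and k = 6 gives 0.030. The smallest intervention counts that reach p<0.05 are:

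| Event-free controls | Event-free intervention families needed | p, 150 per arm | p, 110 per arm |
|---|---|---|---|
| 0 | 6 | 0.030 | 0.029 |
| 1 | 8 | 0.036 | 0.035 |
| 2 | 10 | 0.035 | 0.034 |

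**4. Exact power of that test.** The event-free rates are assumptions, because the protocol gives none. In the first row, power is simply the binomial probability of six or more event-free intervention families at a rate of 2%.

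| Event-free, control vs intervention | 150 per arm | 110 per arm |
|---|---|---|
| 0% vs 2% | 8% | 2% |
| 1% vs 3% | 10% | 4% |
| 1% vs 5% | 40% | 24% |

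**5. The same item with a post-payment window.** Two-proportion z-test, 80% power, two-sided 0.05, with control rates assumed:

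| Control rate | Detectable reduction, 150 per arm | Detectable reduction, 110 per arm |
|---|---|---|
| 30% | 13.6 points | 15.6 points |
| 40% | 15.1 points | 17.4 points |
| 50% | 15.9 points | 18.5 points |
| 60% | 16.1 points | 18.8 points |
| 70% | 15.6 points | 18.3 points |

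The 110-per-arm figures treat dropout as lost information and give multiple imputation no credit.

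**The case against.** **The term is loose, and the statistical analysis plan may define it.** The item repeats neither the definition of homelessness nor a start date. The link to section 6.2 is made only for the primary endpoint. Section 12.4(c) uses study period in connection with payments, which last 24 months, so the term does not always mean 36 months. This is true, but it concerns when the window ends. Nothing in the protocol gives a later start. Opening it at randomization or first payment would change little, because no housing step comes in between.

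**The planning figures seem to imply some zeros.** A negative binomial with mean 52.3 and SD 74.0 has size 52.3²/(74.0² − 52.3) = 0.504 and puts (0.504/52.804)^0.504 = 9.6% of families at zero days. But the protocol takes these figures from prior studies without stating their window or entry condition. They do not show that zeros are to be expected when everyone enters homeless.

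**The assumed rates are unfavorable.** The 1% against 5% case is kinder and is shown above, but it is still underpowered.

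**The consequence is small, and the replacement changes the question.** Both points stand. This is one line in a long list, and no sample size or primary inference rests on it. A window covering months 24 to 36 measures persistence after payments end, and it overlaps with the endpoint on retaining stable housing. A return to homelessness after first stable housing is another possible definition, but it conditions on being housed after randomization, which treatment may itself affect.

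**Conclusion.** The concern holds. As worded, the item is expected to be near 100% in both arms and cannot show an effect of guaranteed income to any useful extent. With event-free rates of 0% to 1% in controls and 2% to 3% in the intervention arm, exact power is 2% to 10%. At 1% against 5% it is 40% with 150 per arm and 24% with 110.

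This rests on three readings: that the item uses the section 6.2 definition, as the primary endpoint does; that the study period opens at or near enrollment; and that few families are housed on the day they enroll. The event-free rates and the control rates are assumptions, while the arm sizes and the dropout rate come from the protocol.

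The primary endpoint and its power are not affected, and the day counts and time to stable housing remain usable. This is a lower-priority correction.

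**What to change.** Before unblinding, replace the open-ended study period in this item with one stated window: any night of homelessness in the 12 months after the 24-month intervention period ends. Add that homelessness is defined by section 6.2. Keep all randomized families in the denominator, in line with the intention-to-treat analysis in section 14.4. Section 14.1 describes a modified set that drops intervention families who do not agree to payments, so the item should say which set applies.

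The data come from the housing questions already scheduled at months 27, 30 and 36. As a side check, Appendix 1 marks the history of homelessness at baseline only, whereas sections 10.2 to 10.8 list the history instruments at every visit. These should be aligned.

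For the four sub-type items, the same window would be consistent. Adjusting for entry sub-type over the full period is an alternative, but families entering in a sub-type would nearly all be events for that item, so a logistic model could come close to separation.

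The cost is low: a wording change to one secondary endpoint, a line on the sub-type items and an alignment of the schedule, with no new visits or participants. The item would no longer cover the payment period, which the day counts and time to stable housing do cover. It would also lean more on multiple imputation, given the assumed 27% dropout.

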4 STUDY DESIGN

4.1 Study Overview

This is a single-site, single-blinded randomized controlled trial. The community partner service organizations, Destination: Home SV and the ¡Sí Se Puede! Collective, have raised funds to provide unconditional cash assistance in the form of guaranteed income (GI) for a period of two years to 150 families with children experiencing homelessness in Santa Clara County and who are eligible for referral to rapid rehousing assistance programs (RRH). The partner service organizations are prioritizing assistance to those awaiting RRH referral given the current extended wait time for RRH services. Because there are far more families who are eligible for GI than there are available resources, 150 eligible families will be randomly selected to receive GI. From the pool of eligible families, we will also randomly select an additional 150 participants as matched controls for the purpose of evaluation.

Thus, we are planning for a total of 300 participants. Participants will be assigned to either the control (usual care) or intervention (guaranteed income) groups in random order. Evaluations will be taken at baseline and every 6 months monthly via in-person and/or telephone assessments.

Screening data will be reviewed to determine participant eligibility. Participants who meet all inclusion criteria and none of the exclusion criteria will be entered into the study.

The following treatment regimens will be used:

- Intervention – guaranteed income, consisting of a total of \$24,000 to be disbursed over 24 months. Participants may opt for either monthly (\$1,000/month) or hybrid (lump sum of \$6,500 the first month, then \$500/month x 11 months for a total of \$12,000 per

year) disbursement schedules, with the option to switch disbursement schedule after the first 12 months. Participants will also be invited to attend a Public Benefits Information Session to learn about public benefits and social assistance programs available to residents of Santa Clara County. Participation in this Benefits Information Session will be optional and not required for study participation.

- Control – usual care as per the partner service organizations. Participants will be invited to also attend a Public Benefits Information Session to learn about public benefits and social assistance programs available to residents of Santa Clara County. Participation in this Benefits Information Session will be optional and not required for study participation.

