8.2 Blinding

Due to the objectives of the study, the identity of intervention and control groups will not be known to investigators or core research staff (i.e., the UCSF study team). Due to the nature of the intervention, participants themselves will not be blinded to whether they are

assigned to the intervention arm. Community partners at Sacred Heart Community Service, who are administering the guaranteed income intervention, will also not be blinded to participants' group assignments. The following study procedures will be in place to ensure single-blinded administration of the study intervention:

Randomization will take place using a computer-generated randomization scheme integrated into the REDCap randomization module, after participants are consented and enrolled into the study. The REDCap randomization module allows specification of which study team members are blinded vs unblinded to group assignments. Because our community partners at Sacred Heart Community Service are administering the guaranteed income intervention, they will be unblinded to group assignments out of necessity, and will receive the information on individuals' group assignments via a UCSF data liaison working with the UCSF study team. The remainder of the core UCSF study team, including the PI and all key personnel (other than the biostatistician, the aforementioned data liaison, and a participant notification liaison) will be unaware and blinded to participant group assignments during the conduct of the study. The study blind will be broken on completion of the study and after the study database has been locked.

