11 ADVERSE EXPERIENCE REPORTING AND DOCUMENTATION

11.1 Adverse Events

The study team will probe, via discussion with the participant, for the occurrence of adverse events (AEs) during each participant visit and record the information in the site's

source documents. Adverse events will be recorded in the patient CRF. Adverse events will be described by duration (start and stop dates and times), severity, outcome, treatment and relation to study intervention, or if unrelated, the cause. For this study, the primary potential adverse events of concern associated with the study intervention are potential loss of existing public benefits and assistance among participants, and increased income tax burden, similar to the risks that would be incurred by the general population in daily life who might experience a similar increase in overall household income.

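### The only adverse-event incidence endpoint counts benefit losses caused by cash payments, so controls cannot have it, and no endpoint compares benefit loss from any cause between arms

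*Protocol*

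**What the plan says.** Section 5.2 ends its list of secondary endpoints with a single adverse-event incidence item: "loss or reduction in public benefits, services and/or assistance directly resulting from receipt of cash payments". Section 4.1 describes the comparator as "Control – usual care as per the partner service organizations"; guaranteed income is given only in the intervention arm.

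Section 11.1 says that "the primary potential adverse events of concern associated with the study intervention are potential loss of existing public benefits and assistance among participants", and adds a higher income tax burden. Section 2.1 names the same two risks. Under 11.1 the study team probes "for the occurrence of adverse events (AEs) during each participant visit" and records, among other things, "relation to study intervention, or if unrelated, the cause". Under 8.2 the core team, apart from the biostatistician, a data liaison and a participant notification liaison, "will be unaware and blinded to participant group assignments during the conduct of the study".

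Several other provisions concern benefits in both arms:

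- Section 5.2 lists "Social service use through self-report and administrative data when available" and, separately, health service use including type of insurance. Neither is limited to effects of the cash.
- Section 9 treats data on public benefits programs as social services data.
- Section 9.1.1 captures the type, frequency and amount of assistance.
- Appendix 1 schedules benefits and social services at all eight assessments.
- Section 14.4 analyses secondary endpoints by intention to treat.

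**The concern.** The causal clause sits inside the endpoint definition. A family that gets no cash cannot lose a benefit because of cash, so the item can be observed in one arm only. In the intervention arm the count depends on someone deciding that the cash caused the loss. Families can also lose benefits for other reasons, such as earnings, recertification or moving out of the county. Some of those losses may be put down to the cash, and some losses that the cash did cause, especially by indirect routes, may not be recognised.

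The blinding rules add a difficulty. The team that elicits adverse events is mostly meant not to know the arm, yet relating a loss to the payments requires knowing or guessing it.

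At stake is the estimate of the harm that section 11.1 puts first. Section 2.1 relies on waivers, counselling and a reimbursement fund to contain it. Randomization could show whether losses still rise despite those measures, but an attributed count cannot.

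**Working it through.** **The plan's own figures.** The protocol gives no rate, precision or power for this endpoint. Its sample-size statement (sections 5.1 and 14.6) concerns days homeless. With SD 74.0 it reproduces: 150 per arm and 24.0 days give 80.2% power; 110 per arm and 28.0 days give 80.1%. Only the arm sizes carry over: 150 as randomized, and about 110 after dropout (300 × (1 − 0.27) = 219, which the protocol takes as 220).

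**Step 1: apply the definition to each arm.** In controls no cash is received, so the count is 0/150 whatever happens to their benefits. In the intervention arm the count is the number of losses judged to result from the cash. The difference between arms is therefore that attributed count itself.

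**Step 2: what a contrast against a fixed zero would do.** By Fisher's exact test, two-sided:

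| Attributed events v 0 | 150 per arm | 110 per arm |
|---|---|---|
| 5 | p = 0.060 | p = 0.060 |
| 6 | p = 0.030 | p = 0.029 |

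Six attributed events are enough for p < 0.05. Now suppose the cash has no true effect, a share b of intervention families lose a benefit anyway, and a share m of those losses is attributed to the cash. The count is then binomial(n, b × m). Both b and m are assumptions.

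| b | m | b × m | P(6 or more), n = 150 | P(6 or more), n = 110 |
|---|---|---|---|---|
| 20% | 25% | 0.050 | 76.6% | 47.3% |
| 10% | 25% | 0.025 | 17.5% | 5.8% |

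These figures show how such a contrast would behave if it were made. The protocol does not say that it will be.

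**Step 3: precision of an any-cause comparison.** With the same rate p in both arms, the 95% half-width is 1.96 × √(2p(1 − p)/n). The range 15% to 25% is assumed.

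| p | n = 150 per arm | n = 110 per arm |
|---|---|---|
| 0.15 | 1.96 × √(0.255/150) = 0.081 | 1.96 × √(0.255/110) = 0.094 |
| 0.25 | 1.96 × √(0.375/150) = 0.098 | 1.96 × √(0.375/110) = 0.114 |

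**Step 4: detectable increase.** This uses the normal approximation for two proportions (pooled variance under the null, two-sided 0.05, 80% power). Control rates are assumed.

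| Control rate | 150 per arm | 110 per arm |
|---|---|---|
| 5% | 9.6 points | 11.7 points |
| 10% | 11.8 points | 14.2 points |
| 20% | 14.4 points | 17.0 points |
| 30% | 15.7 points | 18.4 points |

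An any-cause endpoint would thus give a usable interval but detect only fairly large increases. That is why the fix asks for an estimate with its interval rather than a test.

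**The case against.** A reader might infer that the trial has no randomized comparison bearing on benefit loss at all. The documents do not support that. Social service use and insurance type are secondary endpoints in both arms, analysed by intention to treat, and section 9 counts public benefits data as social services data. Section 11.1 also has unrelated adverse events recorded with their cause, so a control family's loss can be captured. A net fall in benefit receipt could show up as a difference between arms.

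That defeats the strong reading but leaves a gap. Use is not loss. Use may fall because a family no longer needs a service, and it may rise after the benefits information session offered to both arms, which could hide losses.

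Four further objections deserve weight:

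- An attributed count has a purpose, because section 2.1 provides a fund to reimburse unanticipated losses. Section 5.2 also contains items that exist only for recipients, such as the reason for choosing a payment schedule. This stands, and it is why the item should be kept as description.
- The protocol does not say that the item will be tested between arms, and section 14 leaves detail to a statistical analysis plan. That is true, but the causal clause is fixed in the protocol's own endpoint definition.
- A reader might infer that attribution will be guessed, or that it will break the blind. The protocol does not say who makes the judgement, participants know their arm, and some staff are unblinded. What can be said is that the attribution and blinding provisions fit together poorly.
- An any-cause count would include families whose benefits end because income rose, so a success could look like a harm. This is a real cost, met by tabulating losses by reason.

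**Conclusion.** The concern holds in a limited form. The sole adverse-event incidence endpoint cannot occur in controls and so gives no valid between-arm contrast. Benefit receipt is compared only indirectly, and no endpoint defines loss or reduction of benefits regardless of cause.

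The structural zero follows from the wording alone and needs no assumption. Every rate used to size the point is assumed, since the protocol supplies none. On those assumptions, an any-cause risk difference would be estimated to within about 8.1 to 9.8 points at 150 per arm, and 9.4 to 11.4 points at 110 per arm. The change should be made: it concerns the harm named first in section 11.1, and the underlying data are already scheduled in both arms.

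**What to change.** In section 5.2, define the endpoint as any loss or reduction of public benefits, services or assistance from any cause. Derive it the same way in both arms from the benefits data collected at each assessment. Compare randomized arms by a risk difference with a 95% confidence interval, and tabulate losses by reason, for example increased earnings, recertification or a move out of the county.

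Keep losses attributed to cash payments as a separate descriptive item for the intervention arm, assessed by staff whom section 8.2 already leaves unblinded.

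The cost is mainly one reworded endpoint, because benefits and social services are already scheduled at all eight assessments. The reason for a loss would need to be recorded in the same way for both arms; section 11.1 already asks for the cause of unrelated events. The downside is that the any-cause count includes losses unrelated to guaranteed income or due to higher income, so it should be read with the table of reasons.
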